Short Title	Inflatable Helmet for Seizures
IRB Number	824620
Methodology	Open Label Pilot Study
Study Duration	1 year
Study Center(s)	Single Center: University of Pennsylvania
	Part 1:
	To determine reliability in helmet deployment, as evidenced by
	deployment of the helmet during 4 staged falls with normal controls or dummies
	Part 2:
	Primary:
	• To compare rates and types of head injuries and post concussive
	symptoms in seizures resulting in falls occurring while the helmet was
	worn versus seizures resulting in falls occurring while the helmet was
Objectives	not being worn.
	Secondary:
	To determine helmet deployment in seizures versus helmet
	deployment in non-seizure situations.
	To understand adverse events associated with helmet deployment
	during seizures and otherwise.
	To compare rates and types of head injuries and post concussive
	symptoms from seizures leading to helmet deployment versus
	seizures in which the helmet did not deploy. This is contingent on
	there being episodes of helmet non-deployment.
Number of Subjects	Part 1: 4 Part 2: 20
Main Inclusion and	Part 1: Healthy controls
Exclusion Criteria	Part 2: Subjects who experience at least one seizure every 6 months who do not wear static solid helmets.
Investigational Product	Hövding Inflatable Helmet

Duration of administration (if applicable)	Part 1: 1 day Part 2: 6 months
Reference therapy	Static solid helmet
Statistical Methodology	Part 1: the number of times that the helmet deploys in normal controls falling from standing.Part 2: We will compare the rates of injury and post concussive symptoms in patients wearing a helmet during a seizure leading to a fall (independent of whether or not the helmet deployed), compared to patients not wearing a helmet during a seizure leading to a fall. We will also collect the number of days that subjects assigned to wear the helmet wore the helmet.
Safety Evaluations	Medical Record Review, Rivermead Post Concussive Scale, Qualitative Subject Report
Data and Safety Monitoring Plan	The Sponsor-Principal Investigator will conduct a self-assessment to review and evaluate study data and activities. The details of monitoring are included in the Data and Safety Monitoring Plan.

BACKGROUND AND STUDY RATIONALE

This study will be conducted in full accordance all applicable University of Pennsylvania Research Policies and Procedures and all applicable Federal and state laws and regulations.

1 Introduction

Patients with epilepsy often sustain head injuries from the falls that occur during their seizures. While neurologists often advise patients with difficult to control seizures to wear helmets at all times to prevent injuries, patients nearly universally refuse because of social stigma and impracticality. A new, less obtrusive, inflatable helmet has been designed by Hövding Inc. that may encourage increased helmet use; and therefore, potentially result in decreased head injuries caused by seizures.

The primary goal of this study is to estimate effect size and trial outcome instruments to design a study of the safety of a new helmet designed by Hövding Inc. for use in patients with risk of head injury from seizures. The target population with be patients with poorly controlled seizures. Subjects will wear the helmet, fill out a seizure calendar and describe how the helmet reacted during a seizure and during its use in everyday life.

1.1 Background and Relevant Literature

Epilepsy is a common chronic neurological condition defined by recurrent seizures that frequently lead to falls; the original description of epilepsy translated to "The Falling-Down Disease.¹" The CDC estimates that 2.3 million adults in the United States have Epilepsy, with 150,000 people developing the condition each year^{2,3}. The total indirect and direct cost of Epilepsy in the United States is estimated to be \$15.5 billion. Recent studies have concluded that the rates of severe head injuries, lacerations, dislocations, fractures, and drowning in Epileptic patients are higher than their non-Epileptic counterparts^{4,5,6,7}. The risk is increased for children and as well as adults^{8,9}. One study reported that injuries were reported in as many as 15% of epilepsy patients evaluated in an emergency room setting for a seizure¹⁰. This population of patients is also specifically susceptible to head injuries during their seizures. In a recent study that followed 247 Epilepsy patients over 10 years. 16% of patients had seizure related injuries, 79% of which were cranial soft tissue lacerations or contusions¹¹. However, these injuries can be severe and result in traumatic brain injury, skull fractures, and intracranial bleeding.

Helmets are effective in reducing the injuries from serious falls and accidents. A meta-analysis of motorcycle helmets, for example, suggest that they reduce head injuries 69% (OR 0.31, 95% CI 0.25 to 0.38)¹². Moreover, improvements in motorcycle helmet design significantly different (reduced?) rates of facial injury and skull fractures¹³. However, the same attention has not been paid to the helmets used in Epilepsy patients. In one study, 33 institutionalized young patients with drug resistant Epilepsy were provided with helmets to wear. 59 injuries were recorded during the trial, over half of which were scalp and facial bruising, with 48% of those required medical attention. The helmet provided was not in use in 41% of these injuries; and even so, there were not significant differences in rates of laceration, bruising, or the need to seek medical attention at the time of injury in the group wearing helmets versus the group who were not wearing the helmets. This study not only demonstrates the difficulties with static helmet compliance even in a controlled setting but also calls into question whether or not standard static helmets themselves are optimized to prevent injuries during seizures.

Patients with frequent or difficult to control seizures, are often recommended to wear a helmet at all times. Unfortunately, this can result in significant social stigma. The use of static helmets may be a reasonable goal for patients with significant cognitive disability, but is often not acceptable in cognitively normal patients who view them as socially unacceptable and impractical. Consequently, they can accumulate seizure related head injuries and the financial costs resulting from subsequent emergency room visits and hospitalizations.

1.2 Name and Description of the Investigational Product

In 2012, a Swedish company named Hövding began to manufacture a new type of inflatable bicycle helmet. The helmet is designed as a collar with a deployable airbag that inflates when a sensor detects

rapid changes in acceleration. When the rider encounters a crash, the airbag deploys and wraps the back and sides of the users head in inflated nylon fabric which then slowly deflates after deploying. Its design is meant to be unobtrusive and fashion conscious to encourage greater compliance among the cyclist population; it is tested to a higher pounds per square inch standard than the current industry requirements for conventional bicycle helmets. This technology could be adapted to serve as a potential safety device for patients with drug resistant epilepsy (DRE), and patients might use such a device because of its novel, less obtrusive and more fashion conscious design. We believe that use of these helmets by individuals with DRE would reduce the number and severity of head injuries incurred by the DRE population.

1.1.1 Nonclinical Data

The Hövding helmet is currently commercially marketed in Europe. It is CE (Conformité Européenne) marked after undergoing an extensive process for approval by Science Partner Technical Research Institute of Sweden. CE marking is required for a cycle helmet to be able to be sold in Europe and certifies that the helmet complies with the requirements endorsed by the EU Directive for personal protection equipment.

Complete protection in the event of an accident and functioning during normal use are basic criteria for CE marking. For this helmet, "normal use" is defined as wearing the helmet correctly while cycling. All types of helmets have to provide protection for the head in the form of shock absorption and force distribution in an accident to obtain CE marking. The helmet must also be designed so as to cause no unnecessary risks, i.e. there must be no sharp edges, etc. which could injure the wearer. The environmental tolerance criteria for helmets dictate that they must be able to withstand moisture and work in heat and cold and when subjected to the sun's ultraviolet light.

As with many other new types of products launched on the market, for Hövding there was no standard for testing airbag cycle helmets. This meant that SP, which was commissioned to CE mark Hövding, had to develop a new test method in accordance with the requirements of the Personal Protective Equipment Directive, that was adapted for airbag cycle helmets. When the test method had been developed, it was accredited and approved by SWEDAC (the Swedish Board for Accreditation and Conformity Assessment). The test method for Hövding consists partly of tests that are the same as those for traditional cycle helmets, such as an impact test on a flat surface and on a curbstone, and tests relating to the features of an airbag helmet that are unique and that differ from those of traditional cycle helmets. For example, tests are performed to ensure that Hövding inflates when it should, doesn't inflate when it shouldn't and the durability of the airbag fabric¹.

The Hövding helmet is not an approved medical device in the European Union or the United States.

1.1.2 Clinical Data to Date

To date, there is no available clinical research data on the Hövding Inflatable Helmet.

2 Study Objectives

The overall objective is to conduct a pilot study of the use of the Hövding helmet in patients with risk of head injury as a result of seizures to help plan a larger study to determine the safety and efficacy of the helmet for this indication. Ultimately, we hope to demonstrate that its use decreases the rate or severity of head injuries due to seizures that occur from standing. This study will help confirm the assumed safety of this device for use in patients with seizures, estimate the effect size, and pilot the use of novel patient-administered outcome instruments and a previously validated post concussive syndrome scale.

2.1 Part 1 Objectives

2.1.1 Primary Objective

• Reliability in helmet deployment, as evidenced by the deployment of the helmet during 4 staged falls with normal controls or dummies.

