3.1.1.2 Study Intervention Phase

After the study team obtains informed consent and eligibility is confirmed, normal control participants (defined as non-pregnant participants without epilepsy or other diagnosis that may result in falls) will be given helmets and asked to fall straight over onto their right or left side onto a padded surface. Falls will be witnessed and video recorded by the study team. If the participant significantly attempts to break their

fall and the helmet does not deploy, they may be asked to fall again. If the helmet inflates in 3 out of 4 falls, we will proceed with Part 2. If the helmet does not inflate in at least 3/4 falls, we will stop the study.

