3.2 Study Endpoints

3.2.1 Part 1 Endpoints

3.2.1.1 Primary Study Endpoints

The primary endpoint will be the rate of helmet deployment during staged falls.

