4.5 Total Number of Subjects

4.5.1 Part 1

Recruitment will end when 4 subjects are enrolled.

4.5.2 Part 2

Recruitment will end when approximately 20 subjects are enrolled, in order to document at least 5 evaluable seizures during helmet wear.

4.6 Vulnerable Populations:

N/A

5 Study Intervention

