5.1 Description

The Hövding inflatable helmet is designed for cyclists as a collar with a deployable airbag that inflates when a sensor detects rapid changes in acceleration. When the cyclist encounters a crash, the airbag deploys and wraps the back and sides of the user's head in inflated nylon fabric which then slowly deflates after deploying. Its design is meant to be unobtrusive and fashion conscious to encourage greater compliance among the cyclist population; it is tested to a higher pounds per square inch standard than the current industry requirements for conventional bicycle helmets in the EU. Part 1 of this study, where normal controls (or dummies) are asked to fall from standing onto a padded surface while wearing the helmet, will address whether a fall outside of the context of cycling is sufficient for airbag deployment. If so, we will begin part 2 of the study.

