8.3.2 Efficacy Analysis

8.3.2.1 Part 1

• Number of times the helmet deploys in normal controls (or dummies) falling from a standing position.

8.3.2.2 Part 2

- Number of days that subjects in the helmet group actually wore the helmet
- Compare the fraction of the time the device deployed during a seizure that resulted in a fall
- Compare the number of times the helmet deployed in a seizure vs. non-seizure event
- Compare seizures that trigger helmet deployment to those that do not trigger helmet deployment

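### Part 1 is said to determine deployment reliability, but four falls passed at three or more support only a go/no-go screen

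*Combined protocol and SAP*

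**What the plan says.** The Study Summary opens the Part 1 objective with "To determine reliability in helmet deployment, as evidenced by", followed by four staged falls. Section 2.1.1 repeats this as the only Part 1 objective: "Reliability in helmet deployment, as evidenced by the deployment of the helmet during 4 staged falls with normal controls or dummies". Sections 3.2.1.1 and 8.1 make the endpoint a proportion: "The primary endpoint will be the rate of helmet deployment during staged falls". Section 8.3.2.1 plans only a count: "Number of times the helmet deploys in normal controls (or dummies) falling from a standing position". Section 4.5.1 fixes the size: "Recruitment will end when 4 subjects are enrolled". Section 8.2 (sample size and power) is marked N/A, and no target rate, confidence level or error rate is given for Part 1.

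The gate is in section 3.1.1.2: "If the helmet inflates in 3 out of 4 falls, we will proceed with Part 2", and "If the helmet does not inflate in at least 3/4 falls, we will stop the study". Sections 3.1.1.2 and 6.1.1.1 also allow a fall to be repeated when the participant braced and the helmet did not deploy. They do not say how a repeat counts.

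Section 5.1 describes a narrower purpose. It says that Part 1 "will address whether a fall outside of the context of cycling is sufficient for airbag deployment".

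**The concern.** Reliability means that the device deploys in a high proportion of falls. To determine it, a study needs either a target proportion with a rule that separates good devices from poor ones, or an estimate precise enough to be informative. Part 1 has neither. It has four falls, a threshold of three and a bare count.

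Section 1.1.2 says there are no clinical data on this helmet, and section 1.1.1 says that CE marking defines normal use as cycling. Part 1 is therefore the first evidence in these documents on deployment from a standing fall. If a pass is reported under the objective as written, the natural summary is that reliable deployment was shown, and results of three or four out of four cannot support that.

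**Working it through.** The plan gives no precision, power or error rate for Part 1, so there is no figure of its own to reproduce.

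**Inputs.** n = 4 falls (2.1.1, 4.5.1). Pass if X ≥ 3 (3.1, 3.1.1.2). Assumptions not in the documents: a two-sided 95% level, independent falls and one common deployment probability p.

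**Step 1: what a pass says about p.** Exact (Clopper-Pearson) limits:

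- 3/4, lower limit: solve P(X ≥ 3) = 4p³ − 3p⁴ = 0.025, giving p = 0.194. Upper limit: solve P(X ≤ 3) = 1 − p⁴ = 0.025, giving p = 0.975^(1/4) = 0.994. The interval is 19.4% to 99.4%.
- 4/4, lower limit: p⁴ = 0.025, giving p = 0.025^(1/4) = 0.398. The interval is 39.8% to 100%.

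The exact method is the widest of those checked. For 3/4, Wilson gives 30.1% to 95.4%, Agresti-Coull 28.9% to 96.6% and Jeffreys 28.4% to 97.2%. For 4/4, the Wilson lower limit is 51.0%. No method gives an interval narrow enough to call the device reliable.

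**Step 2: how often the gate is passed.** Without repeats, P(pass) = 4p³ − 3p⁴. At p = 0.5 this is 0.5000 − 0.1875 = 0.3125. At p = 0.25 it is 0.0625 − 0.0117 = 0.0508.

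**Step 3: repeat falls.** As an upper bound, suppose every non-deploying fall is repeated once and the better result counts. The per-participant probability becomes q = 1 − (1 − p)², and P(pass) = 4q³ − 3q⁴. At p = 0.5, q = 0.75 and P(pass) = 1.6875 − 0.9492 = 0.7383. At p = 0.25, q = 0.4375 and P(pass) = 0.3350 − 0.1099 = 0.2251. The protocol permits repeats only after bracing, so the truth lies between the two columns.

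**Step 4: the wording in section 9.5.** That section withholds Part 2 if three of the four helmets fail to inflate. Read literally, the study proceeds with two or more deployments: P = 1 − (1 − p)⁴ − 4p(1 − p)³. At p = 0.5 this is 1 − 0.0625 − 0.2500 = 0.6875.

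| True deployment probability | ≥3 of 4, no repeats | ≥3 of 4, every failure repeated once | ≥2 of 4 (literal 9.5), no repeats |
|---|---|---|---|
| 25% | 0.051 | 0.225 | 0.262 |
| 50% | 0.313 | 0.738 | 0.688 |
| 70% | 0.652 | 0.957 | 0.916 |
| 90% | 0.948 | 0.999 | 0.996 |

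**Step 5: Part 2 precision.** Section 4.5.2 aims for at least five evaluable seizures during helmet wear. If all five were falls with deployment, the exact lower limit would be 0.025^(1/5) = 0.478, so even 5/5 gives about 48% to 100%.

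**The case against.** The strongest reply is that this is an openly labelled pilot, and that section 2.1.1 defines its own term: reliability is whatever four staged falls show. The result is used only to decide whether to proceed. For that use the rule works, since without repeats a device with a 25% deployment rate passes only about 5% of the time. This stands, and it is why neither the gate nor the number of falls is criticised here.

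A reader might infer more than the documents support, in four ways:

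- That a printed calculation is wrong. None is, because section 8.2 is N/A and no operating characteristic is claimed.
- That sections 2.1.1 and 5.1 contradict each other. They state purposes of different strength, and both can be pursued with the same falls. It is a mismatch of purpose, and the design supports only the narrower one.
- That the plan carries a Part 1 pass into Part 2 as proof of reliable deployment. It does not. Section 12.1.2 lists non-deployment during a seizure as a foreseeable risk, the Summary plans a comparison contingent on non-deployment, and sections 3.2.2.2 and 8.3 measure deployment per seizure fall afresh.
- That four falls cannot estimate a rate at all. They can, but very imprecisely.

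The objection also limits how the pass probabilities may be used. The no-repeat figures do not describe a procedure that permits repeats, and they assume independent falls with a common probability although controls or dummies may be used.

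What the objection does not remove is the word itself. The Summary says reliability will be determined, and nothing in section 8 qualifies that.

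**Conclusion.** The point holds as a claim that the design cannot deliver. A pass is compatible with a deployment probability of 19% to 99% (3/4) or 40% to 100% (4/4) by the exact method at an assumed 95% level, and the conclusion survives a change of interval method. On the section 3.1.1.2 reading of the gate, a helmet that deploys in half of falls passes about 31% of the time without repeats and at most about 74% with one repeat of every failure. Part 1 remains usable as a screen against gross failure. That defence is strongest when repeats are few and counted separately: at a true rate of 25%, the pass probability is about 5% without repeats and could reach about 23% at the upper bound. The weight is moderate. The correction changes what Part 1 may conclude, and leaves the number of falls and the Part 2 comparisons as they are.

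**What to change.** 1. In the Study Summary and section 2.1.1, replace the reliability objective with the section 5.1 purpose: whether a fall from standing is sufficient to trigger deployment, as a go/no-go screen.
2. In section 8.3.2.1, report x/4 with its exact 95% interval, count first-attempt falls separately from repeats, say how repeats enter the gate, and state that Part 1 does not establish reliability.
3. Keep the no-repeat pass probabilities out of the analysis section. If they are quoted as design properties, state the no-repeat and independent-falls assumptions beside them.
4. Report the Part 2 per-fall deployment rate, already a secondary endpoint in section 3.2.2.2, with its own interval, since about five events will also be imprecise.
5. Reconcile the stopping wording in section 9.5 with that in section 3.1.1.2, so that only one reading is possible.

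The cost is a wording amendment and two interval calculations, with no added falls or participants. The downside for the sponsor is that the stated Part 1 claim becomes less favourable.

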2.2 Part 2 Objectives

2.2.1 Primary Objective

• To compare rates and types of head injuries and post concussive symptoms in seizures resulting in falls occurring while the helmet was worn versus seizures resulting in falls occurring while the helmet was not being worn

2.2.2 Secondary Objective

3 Investigational Plan

3.1 General Design

We propose to investigate the safety of the Hövding helmet device in patients with DRE. While the Hövding helmet is commercially marketed in Europe, it has not been specifically used in a defined epilepsy population. Our project would aim to analyze the safety of the use of the device during 5 seizures from a standing position. For Part 1 of this pilot study, the study team will test helmets on 4 normal controls (or dummies) and have subjects fall directly over onto their sides on a padded floor and record whether or not the helmet deploys. Assuming that the helmet deploys in at least 3/4 of the 4 falls in this scenario as we believe it will, we would proceed to the next phase of the trial.

For Part 2, we propose to enroll 20 subjects from our DRE population who suffer frequent seizures Some patients are already identified and their seizure frequency is documented in a database maintained at the University of Pennsylvania. We will also accept referrals from outside providers and review their records of seizure type, frequency, age, and pregnancy status to see if their patients qualify for the study.

This is a single-center, randomized, 2-way crossover study design. Using block randomization, enrolled participants will be assigned to first enter either the "helmet" or "no helmet" group following consent and confirmation that they meet all inclusion and none of the exclusion criteria. At the time of a seizure that results in a fall, subjects will be asked to fill out a questionnaire to help document the circumstances of the seizure and if any injuries occurred. If the patient seeks medical attention, their medical records will be reviewed afterwards. If a head injury is sustained, they will be asked to fill out the Rivermead Post Concussive scale 48 hours after their seizure in order to quantify their head injuries.² If the subject was wearing a helmet at the time of the fall and it deploys, or of the helmet deploys for any other reason, subject or their representatives will be asked to fill out an additional questionnaire detailing the circumstances of its deployment. After the helmet deploys, we will ask subjects to return their helmets to the University of Pennsylvania for Sponsor assessment. After this fall, or after any helmet deployment, subjects in both groups will be asked to return to the University of Pennsylvania for a study visit during which they will switch groups. If a subject is enrolled for 3 months without experiencing a seizure resulting in fall, they will be considered a screen fail.

During their participation in both groups, subjects will be asked to fill out a daily seizure calendar to help document the frequency of seizures and seizure types.

